3.4.3 Exploratory Endpoints

To assess additional immunogenicity parameters, descriptive central statistics will be presented for the following immunogenicity parameters for the Immunogenicity Population:

- CMV ICS pp65
- CMV ICS gB
- LCMV ELISPOT NP

3.4.4 Subgroups

Should the results be favorable, subgroup analyses and additional analyses may be performed based on patient characteristics, transplant characteristics, number and timing of vaccinations, or use of immunosuppression to identify factors influencing vaccine response. These can be done by summary table using additional stratification factors.

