HB-101 uses replication-deficient lymphocytic choriomeningitis virus (rLCMV) as a vector for a bivalent recombinant vaccine against Human Cytomegalovirus (HCMV). One vector expresses the pp65 protein of HCMV, and one expresses a truncated glycoprotein B (gB) protein of HCMV. The 2 vectors are produced separately. The final drug product is manufactured by mixing 1 batch of rLCMV pp65 and 1 batch of rLCMV gB in a 1:1 ratio based on pp65- and gB-expressing vectors. HB-101 was produced pre-diluted and ready-to-use. HB-101 is formulated at 1.2×10^8 FFU/mL. The product is filled in 2 mL single-dose vials containing 0.7 mL of vaccine. Sodium chloride (0.9% w/v) will be used as the placebo. The sponsor will supply this saline for the study.

2.2.4 *Sample Size Determination*

A total sample size of approximately 150 patients is planned for the study. Patients in Groups 1 and 2 will be randomized with a 2:1 ratio for active versus placebo. Patients in Group 3 will be enrolled to receive open-label HB-101. The sample size has been set for an initial assessment of the safety and immunogenicity of the vaccine candidate, which will provide for approximately 100 patients exposed to the HB-101 vaccine. No formal statistical assessment for sample size determination has been conducted. The sample size is considered adequate to provide the necessary safety and immunogenicity data and help with the determination of point estimates of clinical efficacy endpoints (clinically significant CMV infection as defined by the Food and Drug Administration (FDA) "Guidance for Industry: Cytomegalovirus in Transplantation: Developing Drugs to Treat or Prevent Disease") to design and adequately statistically power Phase 3 trials.

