3.1.4 Hypothesis Testing

There is no formal hypothesis testing for this study. This study is for an initial assessment of the safety and immunogenicity of the vaccine candidate.

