3.4 Endpoint Assessment

The mITT Population will be used for all endpoint analyses related to efficacy, the Safety Population for all endpoint analyses related to safety, and the Immunogenicity Population for all endpoint analyses related to immunogenicity. The results of the study will be analyzed descriptively. However, should the results be favorable, subgroup analyses and additional analyses may be performed based on patient characteristics, transplant characteristics, number and timing of vaccinations, or use of immunosuppression to identify factors influencing vaccine response.

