3.4.1.4 Immunogenicity

To assess the immunogenicity of HB-101, descriptive central statistics will be presented for the following immunogenicity parameters using the Immunogenicity Population:

- CMV neut
- CMV ELISPOT pp65
- CMV ELISPOT gB

The summary will also be based on the number of doses of medication or placebo received (only for 2 and 3 doses). For CMV ELISPOT pp65, CMV ELISPOT gB, and the combination of CMV ELISPOT pp65 and gB, counts and percentages of positive responses will be displayed in addition to the descriptive central statistics. A Wilcoxon signed-rank test will be performed by each treatment and dose group versus the Pre-Dose 1 values from that group. A Mann-Whitney U test of HB-101 versus the corresponding Placebo at each time point will also be performed. The CMV neut parameter will undergo all tests and summaries of the other parameters with the

addition of a 95% confidence interval of the geometric mean titer and a categorical summary of the increase of titer result from Pre-Dose 1 based on the following ranges:

- >2-fold
- >3-fold
- >4-fold

The CMV neut parameter summarization will also be repeated by viremia status (with or without) at Pre-Dose 1 (Group 3 only) and day of transplant.

The result of CMV ELISPOT pp65, CMV ELISPOT gB, pp65 together with gB, and CMV neut result will be plotted against the time of dose received and day of transplant by study medication, dose, and group. The boxplot of CMV neut result by treatment and dose will be provided. The plot of seroconversion rates by dose and treatment will be plotted against the time of dose received and day of transplant. The CMV neutralization antibody titers (NTA) responses and CMV viremia will be plotted by treatment, dose, and viremia status against the time of dose received and day of transplant.

The pre- and post-transplant immunosuppressant use will be summarized by preferred term for all post-transplant randomized patients.

The CMV serology information will be summarized for transplant recipient and kidney donor.

For patients who developed HLA sensitization, the pre- and post-dose sample and recipient genotype information will be listed.

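### Analyses of what drives vaccine response are run only if undefined results are favorable, which makes reporting depend on the outcome and limits what a poor result can teach

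*SAP*

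**What the plan says.** The condition stands in two places. SAP section 3.4 (Endpoint Assessment) says results are analysed descriptively and continues: "However, should the results be favorable, subgroup analyses and additional analyses may be performed". Section 3.4.4 (Subgroups) repeats it: "Should the results be favorable, subgroup analyses and additional analyses may be performed based on patient characteristics, transplant characteristics". Both go on to vaccination number and timing and to immunosuppression, and both give the purpose as "to identify factors influencing vaccine response". Section 3.4.4 adds only that summary tables with extra stratification factors can be used. No factor, cut-point or outcome is named.

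Section 3.1.4 states: "There is no formal hypothesis testing for this study". Section 2.2.4 states: "No formal statistical assessment for sample size determination has been conducted", and says the data are meant to support the design and powering of Phase 3 trials.

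Other breakdowns carry no condition. Section 3.4.1.4 has: "The summary will also be based on the number of doses of medication or placebo received (only for 2 and 3 doses"). It also has: "The CMV neut parameter summarization will also be repeated by viremia status (with or without) at Pre-Dose 1 (Group 3 only) and day of transplant". Section 3.4.2 summarises post-transplant CMV outcomes by doses received, and section 2.2.1 promises a description of how many vaccinations were given and when relative to transplant.

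**The concern.** Whether an analysis is done should not depend on which way the results point. Here it does, on a criterion that nobody can check afterwards. A reader of the study report who finds no subgroup tables cannot tell whether the results were judged unfavorable or the option was simply not used. A reader who finds some cannot tell how the factors were picked from four open families.

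The condition also works against its own purpose. What influences response is at least as useful a question after a weak response as after a strong one. If response is poor, the plan commits to nothing that would show whether it was poor across the board or in, say, older or heavier patients. That matters because the trial exists to inform Phase 3.

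**Working it through.** No figure in the SAP bears on this rule, so the check is a reading of the sections against one another. The only arithmetic concerns the room for judgement and the size of the cells.

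**1. Can *favorable* be given a meaning from the document?** No.
- Section 3.1.4 rules out formal hypothesis testing, so no designated test result supplies one. The nominal Wilcoxon signed-rank and Mann-Whitney tests in section 3.4.1.4 are not linked to the condition.
- Section 2.3 lists two safety endpoints, three primary immunogenicity parameters and five groups of secondary efficacy endpoints: 2 + 3 + 5 = 10 candidates.
- The immunogenicity table in Appendix A gives seven time points after the first dose (pre-dose 2, pre-dose 3, day of transplant, months 3, 6 and 9, end of study). The three primary parameters alone thus give 3 × 7 = 21 readouts, any of which could be called favorable or not.

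**2. Who judges it, and when?** The SAP does not say. Section 2.2.2 allows sponsor team members to be unblinded to each patient after the last dose and the transplant. Section 4.1 allows an interim analysis at a time the sponsor chooses, with the final-analysis methods. The judgement could therefore be made with knowledge of treatment, and more than once.

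**3. What is conditional and what is not?**

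| Factor | Related to response or outcome whatever the result? |
|---|---|
| Number of doses | Yes: sections 3.4.1.4 and 3.4.2 |
| Viremia status | Yes, for CMV neutralization: section 3.4.1.4 |
| Timing of vaccination | Described (section 2.2.1) and used as a plot axis, but no response table by timing |
| Patient characteristics | No |
| Transplant characteristics | No |
| Immunosuppression | No: section 3.4.1.4 only tabulates its use |

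The gap is the last four rows, not the whole of the subgroup question.

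**4. Which factors are fixed before randomisation?** Appendix A places randomisation on or before Day 0. Group 1 versus Group 2 is set at enrollment, age is taken at informed consent, and sex and screening BMI are baseline (section 3.3.4). Number and timing of vaccinations come after randomisation. Transplant characteristics are recorded at the day-of-transplant visit, also after it. Induction therapy belongs with them. HLA mismatch may too, because section 2.2.1 allows a deceased donor to replace the planned living donor.

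**5. How small are the cells?** About 150 patients, at least 15% of them in Group 3, and 2:1 allocation in Groups 1 and 2:
- Group 3: at least 0.15 × 150 = 22.5.
- Groups 1 and 2: at most 150 − 22.5 = 127.5.
- Placebo: at most 127.5 / 3 = 42.5, or about 43.

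An even two-way split leaves about 21 placebo patients per cell. The mITT Population, which needs a transplant and at least two prior doses, can only be the same size or smaller.

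**The case against.** The best defence is that this is a descriptive Phase 2 trial, the paragraph is optional, and no endpoint, population or estimate depends on it. That is correct, and it caps the seriousness of the point. It does not justify the condition: exploratory status is a reason to limit the number of analyses, not to do them only after good news.

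Three stronger readings are tempting, and the document does not support them.

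- *The plan prevents the trial from explaining a poor response.* It does not. The breakdowns by number of doses and by viremia status are unconditional, all data are listed (sections 3.1.3 and 5), and nothing forbids further work after an unfavorable result. The plan merely commits to none on the remaining factors.
- *The harm can be expressed as a chance of a false-positive subgroup.* A reader might apply the usual formula for several independent tests at the 5% level. No subgroup tests are planned; section 3.4.4 speaks of summary tables. The number of factors would also have to be invented. And the formula measures multiplicity, not the effect of the condition: it would give the same answer if the condition were deleted. Selecting on a good overall result can inflate effects within subgroups, but does not in general inflate the contrast between them.
- *Subgroup analyses that are performed will be hidden.* The SAP does not say so. The problem is that whether they are done at all depends on the result.

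The objection about thin cells stands. It argues for a short list.

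**Conclusion.** The point holds as a fault in a stated rule, not as missing detail. Sections 3.4 and 3.4.4 make analyses of response by patient characteristics, transplant characteristics, timing of vaccination and immunosuppression depend on results that are favorable in an undefined sense, and optional even then. The effect is result-dependent reporting and a limited ability to learn from a poor response.

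Its size cannot be given as a number. It touches no primary or secondary estimate and no error rate; the damage is to interpretation and to the Phase 3 planning that section 2.2.4 gives as a purpose of the data. It should be corrected, but it does not threaten the main results. The conclusion rests on the wording of the two sections and on no other part of the SAP defining the trigger; none was found. The cell sizes assume enrollment of 150 with Group 3 at its 15% minimum.

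**What to change.** 1. Delete the opening condition in both section 3.4 and section 3.4.4.
2. Commit to a short list of factors already collected and fixed before randomisation, for example Group 1 versus Group 2, age, sex and BMI category. Section 3.3.4 already splits BMI at 30 kg/m²; a cut-point for age has to be set in advance.
3. By each factor, and whatever the overall result, tabulate CMV neutralization, ELISPOT pp65 and ELISPOT gB at the day of transplant, and post-transplant CMV infection. Four factors by four outcomes is 16 breakdowns, which fit in four tables.
4. Label factors fixed after randomisation as descriptive only: number and timing of vaccinations, induction therapy and other transplant characteristics. Those that describe the operation itself, such as ischemia times, cannot have influenced the day-of-transplant sample, which is taken before the procedure; they belong with post-transplant outcomes.
5. State that any further subgroup work will be reported as post hoc.

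The cost is SAP wording before database lock and a few tables. The downside is small cells, with at most about 43 placebo patients before any split, so the tables should show counts and be read as description.

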3.5 Safety Assessment

These additional safety data will be summarized based on the Safety Population.

3.5.1 Vital Signs

Vital signs including height, weight, systolic blood pressure, diastolic blood pressure, heart rate, respiratory rate, body temperature will be summarized by descriptive statistics for each treatment group. Both actual values and changes from baseline over time will be summarized.

3.5.2 Physical Examinations

The overall physical examination result at each time point will be summarized with counts and percentages.

4 ANALYSIS TIMING

4.1 Interim Analysis

An interim analysis may take place for this study at a timepoint determined by the Sponsor.

Derivations and definitions for the interim analysis will be based on those required for the final analysis contained in this analysis plan, unless deviations are stated within the text. The list of outputs provided with the full set of output templates (planned for the final analysis) will highlight which of these outputs will also be provided for the interim analysis.

Methods for handling the interim analysis are same as the final analysis discussed in Section 3.

5 PROGRAMMING SPECIFICATIONS

Analyses will be performed using SAS® version 9.4 or higher. All available data will be presented in patient data listings which will be sorted by patient and visit date as applicable. Detailed Programming Specifications will be provided in a separate document.

APPENDIX A: SCHEDULE OF EVENTS

Study Events Pre-Transplant

Pre-Transplant Study Visit ^{1,2,3,4,5,6}	1	2	Phone Call	3	4	Phone Call	5	6	Phone Call	7	8	9
Time frame of study assessment from study drug injection	Screening ⁷	Day 0 Dose 1	3 Days After Dose 1 ⁸	7 Days After Dose 1 ⁹	28 Days After Dose 1 ^{10,16} Dose 2	3 Days After Dose 2 ⁸	7 Days After Dose 2 ^{9,11}	Dose 3 ^{10,16}	3 Days After Dose 3 ⁸	7 Days After Dose 3 ^{9,11}	Day of Transplant (Prior to Transplant Procedure)	30 Days After Last Dose of Study Drug (HB-101 or placebo) ¹¹
Study Assessments												
Informed consent	X ¹⁴											
CMV serology	X ¹⁴											
Inclusion/exclusion criteria	X ¹³	X ¹²										
Demographics	X ¹⁴											
Pregnancy test (serum or urine hCG) (for females of childbearing potential) ²¹	X ¹³	X ¹²			X ¹²			X ¹²			X	X
Serum FSH ¹⁹	X ¹³											

Pre-Transplant Study Visit^{1,2,3,4,5,6}	1	2	Phone Call	3	4	Phone Call	5	6	Phone Call	7	8	9
Time frame of study assessment from study drug injection	Screening⁷	Day 0 Dose 1	3 Days After Dose 1⁸	7 Days After Dose 1⁹	28 Days After Dose 1^{10,16} Dose 2	3 Days After Dose 2⁸	7 Days After Dose 2^{9,11}	Dose 3^{10,16}	3 Days After Dose 3⁸	7 Days After Dose 3^{9,11}	Day of Transplant (Prior to Transplant Procedure)	30 Days After Last Dose of Study Drug (HB-101 or placebo)¹¹
Relevant medical history	X ¹³	X ¹²										
Medication/vaccination history	X ¹³											
Vital signs (SBP, DBP, heart rate, respiratory rate, and body temperature)		X ¹²		X	X ¹²		X	X ¹²		X	X	X
Physical examination	X ¹³	X ¹²			X ¹²			X ¹²			X	X
Randomization (Groups 1 and 2 only)		X ^{12,15}										
Study drug (HB-101 or placebo) injection		X			X			X				
On-site post-injection observation (60 minutes)		X			X			X				
Study drug (HB-101 or placebo) injection site examination for reactogenicity		X		X ¹⁷	X		X ¹⁷	X		X ¹⁷		

Pre-Transplant Study Visit^{1,2,3,4,5,6}	1	2	Phone Call	3	4	Phone Call	5	6	Phone Call	7	8	9
Time frame of study assessment from study drug injection	Screening⁷	Day 0 Dose 1	3 Days After Dose 1⁸	7 Days After Dose 1⁹	28 Days After Dose 1^{10,16} Dose 2	3 Days After Dose 2⁸	7 Days After Dose 2^{9,11}	Dose 3^{10,16}	3 Days After Dose 3⁸	7 Days After Dose 3^{9,11}	Day of Transplant (Prior to Transplant Procedure)	30 Days After Last Dose of Study Drug (HB-101 or placebo)¹¹
(assessment of local and general symptoms)												
Patient's blood sample for humoral immunogenicity		X ¹²			X ¹²			X ¹²			X	
Safety blood collection (CBC with differential, liver function tests and enzymes, renal function tests)	X ¹³	X ¹²		X ¹⁸	X ¹²		X ¹⁸	X ¹²		X ¹⁸	X	X
All concomitant medications		X	X	X ¹⁷	X	X	X ¹⁷	X	X	X ¹⁷	X	X ²⁰
Record adverse events		X	X	X ¹⁷	X	X	X ¹⁷	X	X	X ¹⁷	X	X
Record SAEs		X	X	X ¹⁷	X	X	X ¹⁷	X	X	X ¹⁷	X	X
Transplant characteristics											X	

1. After transplant, patients will be assessed per the study visits in Table 6 (all patients of the study who receive study drug). Remaining pre-transplant phone calls/study visits will occur post-transplant and will not be protocol deviations.

2. During the study, it is possible that the time windows of study visits and assessments will be redundant. If the time window is ± 2 weeks, assessments should NOT be duplicated.

3. If kidney transplant occurs prior to Day 34, the patient will be administered study drug (HB-101 or placebo) at Day 0 only. A minimum of 7 days (± 2 days) must be planned between the last dose of study drug and transplantation.

4. If kidney transplant occurs between Day 35 and Day 62, the patient will be administered study drug (HB-101 or placebo) at Day 0 and Day 28. A minimum of 7 days (± 2 days) must be planned between the last dose of study drug and transplantation.
5. If kidney transplant occurs between Day 63 and Day 90 or between Day 91 and Day 120, the patient will be administered study drug (HB-101 or placebo) at Day 0, Day 28, and Day 56 or Day 84. A minimum of 7 days (± 2 days) must be planned between the last dose of study drug and transplantation.
6. There is a ± 3 day window on assessments during the pre-transplant Treatment Period, to take into account public or religious holidays or weather, if not explicitly specified otherwise.
7. During the study, the Screening Period should be within 56 days of Day 0.
8. Time (window) from the last dose of study drug (HB-101 or placebo) is 3 days (± 1 day).
9. Time (window) from the last dose of study drug (HB-101 or placebo) is 7 days (± 3 days).
10. Time (window) of study drug (HB-101 or placebo) is 28 days (± 7 days) from Dose 1 to Dose 2 and 28 or 56 days (± 7 days) from Dose 2 to Dose 3 (depending on the transplant date).
11. In some cases, the post-injection follow-up visits will occur post-transplant.
12. Assessments occur prior to study drug (HB-101 or placebo) injection.
13. Assessments can be conducted for up to 14 days prior to Day 0.
14. Assessments can be conducted for up to 56 days prior to Day 0.
15. Randomization will only occur for patients in Groups 1 and 2 and should occur prior to or on Day 0 pre-dose.
16. After Day 0 dose administration, a timeframe of ± 7 days from scheduled day of dosing is allowed.
17. In the event that the patient cannot return to the site for the study visit, the assessments will be collected via phone call.
18. In the event that the patient cannot return to the site for the study visit, every effort should be made to collect local safety blood collection tests and enter these into the eCRF, as well as assess for clinical significance by the investigator.
19. Only for female patients aged ≤ 50 years with 6 months of spontaneous amenorrhea.
20. If the 30-day post-injection follow-up visit occurs post-transplant, then only concomitant medications of special interest and those related to SAEs need to be recorded.
21. Urine pregnancy test will be limited to patients producing urine daily. CBC = complete blood count; CMV= cytomegalovirus; Day 0 = day of first dose of study drug; Day 28 = 28 days after the first dose of study drug; Day 34 = 34 days after the first dose of study drug; Day 35 = 35 days after the first dose of study drug; Day 56 = 56 days after the first dose of study drug; Day 62 = 62 days after the first dose of study drug; Day 63 = 63 days after the first dose of study drug; Day 84 = 84 days after the first dose of study drug; Day 90 = 90 days after the first dose of study drug; Day 91 = 91 days after the first dose of study drug; Day 120 = 120 days after the first dose of study drug; DBP = diastolic blood pressure; eCRF = electronic case report form; FSH = follicle-stimulating hormone; hCG = human chorionic gonadotropin; SAE = serious adverse event; SBP = systolic blood pressure.

Study Events Post-Transplant (All Patients of Study Who Received Study Drug)

	Follow-Up Visit ² Monthly				Follow-Up Visit 3 Months After Transplant ¹	Follow-Up Visit 6 Months After Transplant ¹	Follow-Up Visit 9 Months After Transplant ¹	End of Study Visit ³
	Week 1	Week 2	Week 3	Week 4				
Study Assessments^{4,5}								
Pregnancy test (serum or urine hCG) (for females of childbearing potential) ⁷					X	X	X	X
Physical examination					X	X	X	X
Patient's blood sample for humoral immunogenicity					X	X	X	X
Patient's blood sample for cellular immunogenicity					X	X	X	X
Record adverse events Record adverse events -Adverse events, regardless of causality, should be recorded up through 30 days after the last injection of study drug. -Adverse events considered related to the study drug should be recorded from 31 days after the last injection of study drug up through the End of Study Visit.	<-----X-----> Ongoing during study				<-----X-----> Ongoing during study			
Record SAEs	<-----X-----> Ongoing during study				<-----X-----> Ongoing during study			
Concomitant medications related to SAEs	<-----X-----> Ongoing during study				<-----X-----> Ongoing during study			
Concomitant medications of special interest -Anti-virals and immunosuppressants, non-study vaccines, granulocyte colony-stimulating factor, erythropoietin, and transfusions of blood product taken 7 days prior to and after transplant.	<-----X-----> Ongoing during study				<-----X-----> Ongoing during study			
Record adverse events of special interest:	<-----X-----> Ongoing during study				<-----X-----> Ongoing during study			
Graft rejection assessments	Transplant Follow-up visits per institutional standard.							X

CMV disease and syndrome assessments	Transplant Follow-up visits per institutional standard.							X
Blood sample for CMV PCR local testing: ⁶								
Patients to be followed preemptively post-transplant for the first 16 weeks after transplant.	X	X	X	X	X	X	X	X
Patients to be treated prophylactically with anti-virals post-transplant.	Time points following institution's standard of care.				X	X	X	X
Blood sample for central CMV PCR analysis	Study site personnel will draw the patient's blood sample for central CMV PCR analysis when local CMV PCR testing is conducted at the institution.				X	X	X	X

1. Time window of follow-up visits after transplant is ± 7 days.
2. Follow-up visits will occur per institutional standards of post-transplant clinical monitoring after discussion with the sponsor.
3. Per Section 6.4, the End of Study Visit is also the 12 months post-transplant follow-up visit.
4. During the study, it is possible that the time windows of study visits and assessments will be redundant. If time window is ± 2 weeks, assessments should NOT be duplicated.
5. There is a ± 7 day window on assessments during the post-transplant Follow-Up Period, to take into account public or religious holidays or weather, if not explicitly specified otherwise.
6. Only 1 post-transplant CMV management strategy will be followed (preemptively or prophylactically).
7. Urine pregnancy test will be limited to patients producing urine daily. CMV = cytomegalovirus; hCG = human chorionic gonadotropin; PCR = polymerase chain reaction; SAE = serious adverse event.

Immunogenicity Analysis and Time Points

	Pre-Dose 1¹	Pre-Dose 2¹ (28 Days After Dose 1²)	Pre-Dose 3¹	Day of Transplant (Prior to Transplant Procedure)	3 Months After Transplant³	6 Months After Transplant³	9 Months After Transplant³	End of Study Visit
Study Assessments								
Study drug injection	X	X	X	-	-	-	-	-
Immunogenicity Testing								
CMV neut	X	X	X	X	X	X	X	X
LCMV neutralizing antibody	X	-	-	X	-	-	-	X
CMV ELISPOT pp65	X	X	X	X	X	X	X	X
CMV ELISPOT gB	X	X	X	X	X	X	X	X
CMV ICS pp65	X	X	X	X	X	X	X	X
CMV ICS gB	X	X	X	X	X	X	X	X
LCMV ELISPOT NP*	X	X	X	X	X	X	X	X

*Possible that analyses will not occur at all time points, e.g., insufficient volumes of blood. 1. Blood collection for immunogenicity will be performed prior to each study drug booster administration. 2. Time (window) from the last dose of study drug (HB-101 or placebo) is 28 days (± 7 days). 3. Time window of follow-up visits after transplant is ± 7 days. CMV = cytomegalovirus; ELISPOT = enzyme-linked immunospot; gB = glycoprotein B; ICS = intracellular cytokine staining; LCMV = lymphocytic choriomeningitis virus; neut = neutralization; NP = nucleoprotein; pp65 = phosphoprotein 65 kD

